Substance Use Prevention Campaign for American Indian Youth

NCT03051633

May 21, 2020

The Be Under Your Own Influence substance use prevention intervention and its assessment will include the following key features.

- A randomized cluster design will be used where treatment schools receive an intervention targeted to 7th grade students, and control schools receive no intervention. The intervention will be implemented with 2 cohorts of 7th graders. Cohort 1 will receive the intervention in parts of years 2 and 3 of the grant while cohort 2 will receive the intervention in parts of years 3 and 4.
- The intervention will be built around the successful school-based anti-drug campaign, Be Under Your Own Influence (BUYOI). It will be adapted for use in reservation-based AI schools and communities to reduce substance use among 7th graders. The intervention uses older peers to deliver messages targeting the goals of autonomy and achievement (aspirations) associated with a drug-free life.
- Years 1 and 2 will be spent working as partners with the treatment schools and communities to adapt the intervention so that it is both culturally appropriate and powerful. We will seek regular and extensive feedback from both adults and youth in the treatment communities. This will include regular meetings with Community Advisory Boards and use of Participatory Action Research (PAR) methods with youth, including a photovoice project, to engage these youth in substance abuse prevention efforts. Local AI liaisons will assist in organizing and implementing the activities that will occur in the intervention communities, including formation of the advisory group, recruitment of students into the project, organization of focus groups, and recruiting the school staff who will serve as advisors to the high-school students.
- In the summer prior to the implementation of the intervention for cohort 1, we will hold a 7-day training institute at Colorado State University for the high school youth selected to be role models. Seven students from each of the four communities randomly selected as intervention sites (28 students) will participate in the institute. During the institute, these youth will be trained to serve as peer role models and to plan and conduct the intervention. During this time, results of a photovoice project will be used to adapt print, audio, and visual media products that the students will use in delivering the campaign messages. A significant portion of the institute will engage the youth as active participants in creating the intervention products. Training modules at the institute will be recorded, edited, and prepared into a training program that can be delivered on-site at the intervention schools the following year for cohort 2.
- Data collection will consist of 4 longitudinal measurement occasions for each cohort using the adapted American Drug and Alcohol Survey. Longitudinal growth models will test for effects of the intervention on the targeted outcomes.
- A sustainable, turnkey intervention will be developed that can be adapted and implemented in AI communities across the nation. If this intervention is found to be effective, we will develop electronic campaign materials that can be adapted for local use. These will be made widely available and easily accessible via a website.

Statistical Analysis

Given the discrete characterization of time as interval-censored risk-periods in this longitudinal intervention study, we will use complementary log-log discrete time hazard models, implemented within R, to estimate the effects of BUYOI and the covariates on the risk of first-time alcohol use, alcohol intoxication, and marijuana use during students 7th-8th grade school years. A discrete time hazard model is an optimal approach to analyzing longitudinal data characterized by non-continuous time (Singer & Willer, 2003). In the present study, the discrete time hazard represents the conditional probability that a student will experience first time alcohol

use, intoxication, or marijuana use (assessed as separate outcomes) during a measurement period, given that students did not use a substance during a previous measurement period. Each variable in the model is considered time-invariant for the purpose of this analysis. Thus, for each model, we tested 1) the hypothesized main effects of BUYOI, gender, and perceived consequences of use for aspirations and autonomy controlling for age and treatment exposure, and 2) the two-way interaction between gender and treatment.

Measures

Age at baseline is included as a covariate in all models. Predictors to be included in our model are sex (Male / Female), perceptions of alcohol / marijuana use consequences for autonomy, and perceptions of alcohol/marijuana use consequences for future aspirations. Perceptions of impact on autonomy is measured with 4 items on a 5-point Likert scale (1 = strongly disagree, 5 = strongly agree), with items including "A way to be true to myself is to NOT [drink alcohol / use marijuana]. Perceptions of use on future aspirations is measured with 3 items on a 5-point Likert scale (1=strongly disagree 5 = strongly agree), with items including "One thing that could keep me from doing what I want to do is [drinking alcohol / using marijuana]". For both measures, larger scores reflect stronger perception of consequences for use. Outcomes include hazards of first-time alcohol use, alcohol intoxication, and marijuana use.

Event Variable. Three dichotomized variables calculating self-reported first-time alcohol use, alcohol intoxication or marijuana in the months prior to each measurement occasion, where participants did not report substance use during a prior measurement occasions of this four-wave (i.e. four measurement occasion) longitudinal study. That is, first time substance use reported at measurement occasion 2 after no lifetime use reported at baseline, reported use at occasion 3 after none reported at occasion 2 or baseline and reported use at occasion 4 with none reported prior to occasions 3, 2 or baseline.

Episodes. In this study, episodes represent the period of time between measurement occasions, as such, each episode represents the measured period of time between each wave of assessments. The event variable represents whether or not the participant experienced first-time substance use uptake prior to each assessment.

Duration Variable. Duration of participation in media campaign intervention period across all four waves, beginning with the transition from first to second wave of data collection.

Censoring Indicator. If no substance use is reported, censoring indicator represents completion of study at wave 4. If substance use is reported, censoring indicator indicates the risk period (the period of time between waves 1 and 2, 2 and 3, or 3 and 4) during which the participant experienced uptake of substance use. Approximately 10.3% ($n = 51$), 20.1% ($n = 100$) and 4.6% ($n = 23$) of participants reported lifetime alcohol use, marijuana use or alcohol intoxication at baseline, respectively. As such, these participants are censored (excluded) from the analysis at baseline. Of note, censoring is specific to each model. For example, if a student reported lifetime alcohol use at baseline, but did not report lifetime alcohol intoxication or lifetime marijuana use, that student is censored at baseline in the alcohol initiation model but remains uncensored within the other two models.

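### The hazard models list no cohort term, although two cohorts a year apart with differently trained role models appear to be analysed together, and baseline exclusions are not split by arm or cohort

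*Combined protocol and SAP*

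**What the plan says.** The opening list of key features sets out a cluster-randomized design in which "treatment schools receive an intervention targeted to 7th grade students, and control schools receive no intervention". It continues: "The intervention will be implemented with 2 cohorts of 7th graders". On timing, "Cohort 1 will receive the intervention in parts of years 2 and 3 of the grant", and "cohort 2 will receive the intervention in parts of years 3 and 4".

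The cohorts' role models are prepared differently. For the first, "In the summer prior to the implementation of the intervention for cohort 1, we will hold a 7-day training institute"; the modules are then recorded and "prepared into a training program that can be delivered on-site at the intervention schools the following year for cohort 2". Four communities are randomly selected as intervention sites.

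The Statistical Analysis section describes a complementary log-log hazard model for each of three outcomes, over 7th and 8th grade. It tests "the hypothesized main effects of BUYOI, gender, and perceived consequences of use for aspirations and autonomy controlling for age and treatment exposure", plus gender by treatment, with every variable held fixed over time. Treatment exposure is not defined.

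Under Measures (Censoring Indicator), lifetime use at baseline was reported by 51 students for alcohol (10.3%), 100 for marijuana (20.1%) and 23 for intoxication (4.6%), and "these participants are censored (excluded) from the analysis at baseline", separately for each model. No count is split by arm or cohort, and no survey dates are given.

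**The concern.** Cohort is a known design factor. It carries the calendar year, the way the role models were trained, and how long the campaign had been running in the school. A model without it leaves any year-to-year change in first use in the noise or, if the arms differ in cohort mix, in the BUYOI estimate. A model without BUYOI-by-cohort gives one hazard ratio and cannot show whether the effect persists when training is delivered on site.

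A second issue is less certain. If cohort 2 is first surveyed after the campaign has started in its schools, the rule that removes baseline users acts on a variable that treatment may already have changed, in one arm only. The treated and control risk sets would then no longer be comparable by randomization.

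**Working it through.** **1. Reproduce the exclusion figures.** The denominators that round correctly are 493–497 for 51 at 10.3%, 497–498 for 100 at 20.1%, and 495–505 for 23 at 4.6%. Only N = 497 fits all three. The at-risk sets are 497 − 51 = 446, 497 − 100 = 397 and 497 − 23 = 474. One denominator with no cohort split fits a pooled analysis but does not prove it.

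**2. Timing of cohort 2's baseline.** Cohort 2's campaign starts a year after cohort 1's, in the same intervention schools. The Duration Variable starts the campaign period between waves 1 and 2, and the risk window is 7th–8th grade. Wave 1 for cohort 2 is therefore very likely at or near its own 7th-grade start, after cohort 1's campaign began. This is an inference.

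**3. Can a listed term stand in for cohort?**
- Age: both cohorts are 7th graders, so baseline age does not identify the cohort.
- Episode: it counts between-wave periods within a student's own follow-up, not calendar years.
- Treatment exposure: undefined and time-invariant, so it cannot be credited.
- Duration Variable: it runs from each student's own wave 1–2 transition and carries no calendar year.

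**4. Effect of omitting cohort.** Let c be the cohort 2 to cohort 1 hazard ratio and q_T, q_C the cohort 2 shares by arm. To a first approximation the BUYOI hazard ratio is multiplied by [1 + q_T(c − 1)] / [1 + q_C(c − 1)]. This is 1 if q_T = q_C or c = 1. The documents give none of these quantities.

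**5. What a single estimate can hide (assumed hazard ratios).** With 0.70 in cohort 1 and 0.85 to 1.00 in cohort 2, equal weights on the log scale give √(0.70 × 0.85) = 0.77 to √(0.70 × 1.00) = 0.84. The upper value describes neither cohort.

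**6. Selection at baseline (illustrative).** Take p as the baseline use figure. Assume spillover cuts pre-baseline use in treated cohort 2 schools by 10% to 30% (r = 0.9 to 0.7), that students retained as a result have h = 2 to 4 times the hazard of the others, and that there is no other effect.
- Retained share s = p(1 − r)/(1 − pr).
- Cohort 2 hazard ratio = 1 + s(h − 1).
- Pooled hazard ratio = square root of that, for equal cohorts.

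| Outcome | p | s | Cohort 2 | Pooled |
|---|---|---|---|---|
| Alcohol | 0.103 | 1.1–3.3% | 1.01–1.10 | 1.01–1.05 |
| Marijuana | 0.201 | 2.5–7.0% | 1.02–1.21 | 1.01–1.10 |
| Intoxication | 0.046 | 0.5–1.4% | 1.00–1.04 | 1.00–1.02 |

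For the marijuana maximum: s = 0.201 × 0.3/(1 − 0.201 × 0.7) = 0.0603/0.8593 = 0.070, and 1 + 0.070 × 3 = 1.21. Other assumptions (a 10–50% cut, h = 1.5 to 3) give pooled maxima of 1.05, 1.11 and 1.02 in the same order.

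**7. The opposing force.** Spillover would also mean earlier exposure, which could lower later hazard in treated students. A reduction of 1 − 1/1.02 = 2% to 1 − 1/1.21 = 17% would cancel the marijuana range in step 6, and a larger one would reverse it.

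**8. Would the exclusion counts detect it?** Assume four equal arm-by-cohort cells, 497/4 ≈ 124. The 95% half-width for a difference in marijuana use is 1.96 × √(2 × 0.201 × 0.799/124) ≈ 10 points before clustering. A 10–30% cut is 2 to 6 points. The counts can describe an imbalance but cannot rule spillover out.

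**The case against.** Schools are randomized and the treatment schools run both cohorts. If control schools also supply both in similar proportions, cohort is roughly balanced and its omission confounds little. That stands: the covariate mainly guards against chance imbalance and reduces noise. It does not repair a demonstrated bias.

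A reader might infer that the BUYOI estimate is biased toward no effect. The documents do not support this. The campaign is aimed at 7th graders, and nothing says that younger students share the building or see the materials. Without spillover there is no selection bias; with it, the two forces in step 7 act in opposite directions. The formula in step 6 also ignores depletion: with assumed per-period hazards of 5–15%, the marijuana maximum of 1.21 falls to 1.17–1.20 in the first period and 1.07–1.15 in the third.

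A reader might also infer that the cohorts received different campaigns. The text shows a difference in how role models were trained, not in what 7th graders received. Nor does it tie the planned turnkey product to cohort 2's version; that product is described as electronic materials on a website.

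Finally, cohort 1 is not clearly untouched at baseline, because adaptation and photovoice work took place in the treatment communities in years 1 and 2. This also stands and limits what a cohort 1 analysis can show.

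**Conclusion.** The omission is real and can be checked in the text: two cohorts a year apart, differently trained role models, and no cohort or BUYOI-by-cohort term. Pooling is implied by one model per outcome and one set of counts; it is not stated. The likely consequence is added noise or chance imbalance in the BUYOI estimate, of a size the documents do not allow one to calculate, and no view of whether the effect holds under on-site training.

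Treatment-dependent exclusion in cohort 2 is a possibility only. It rests on an inferred survey date and an unstated spillover. The illustrated pooled shifts, at most about 1.11 for marijuana, 1.05 for alcohol and 1.02 for intoxication, depend wholly on assumed inputs and cover only one of two opposing forces. This is a nearly free improvement of low severity.

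**What to change.** - Add cohort as a fixed covariate in all three hazard models.
- Report BUYOI-by-cohort and a cohort 1 estimate as supportive analyses. State that both are imprecise with four intervention communities, that a cohort difference would mix training mode with calendar year and prior campaign activity, and that cohort 1's baseline may itself follow the year 1–2 adaptation and photovoice work.
- Tabulate baseline lifetime users excluded, by arm and cohort, for each outcome. Treat the table as descriptive; a rule triggered by an arm difference would have little power.
- State the survey dates for each cohort and define treatment exposure.

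I would not recode cohort 2 baseline users as first-period events: lifetime use mostly covers years before the campaign existed.

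The cost is one parameter in each main model, two imprecise supportive estimates and one table, with no new data. Because the section already uses the past tense for the model tests and reports observed counts, the SAP should record when these terms were added relative to sight of the outcome data.

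### The trial randomises clusters, but neither the hazard models nor the growth models specify any adjustment for clustering; run as written, they understate the BUYOI standard error at any positive ICC

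*Combined protocol and SAP*

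**What the plan says.** The first design bullet in the key features reads "A randomized cluster design will be used where treatment schools receive an intervention targeted to 7th grade students"; control schools receive nothing. The training-institute bullet describes allocation by community: "Seven students from each of the four communities randomly selected as intervention sites (28 students". The number of control clusters is not given, and the plan does not say whether school and community are the same unit. They would be if each community has one school.

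Under Statistical Analysis the plan states "we will use complementary log-log discrete time hazard models, implemented within R, to estimate the effects of BUYOI and the covariates", for three separate outcomes: first alcohol use, first intoxication and first marijuana use. The terms tested are "the hypothesized main effects of BUYOI, gender, and perceived consequences of use for aspirations and autonomy controlling for age and treatment exposure", followed by a gender-by-treatment interaction. The Measures section adds only "Age at baseline is included as a covariate in all models".

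The data-collection bullet in the key features names a second analysis: "Longitudinal growth models will test for effects of the intervention on the targeted outcomes". That one sentence is its whole description.

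No section mentions a school or community effect, frailty, GEE, robust variance, cluster-level analysis, ICC or design effect. The Duration Variable and treatment exposure describe participation in the campaign and do not identify clusters.

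**The concern.** BUYOI is assigned to whole clusters, so the evidence about its effect comes from comparing a small number of clusters. Students in one community share peers, staff, norms and access to substances, and their outcomes are likely to be correlated. A model that treats them as independent counts between-cluster variation as if it averaged out over several hundred separate students. The BUYOI confidence interval is then too narrow and its p-value too small in all three outcome models, and a chance difference between communities is more easily read as a campaign effect.

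The consequence is practical. The key features make wide release of the campaign materials depend on the intervention being found effective, and no primary model is named. Neither named analysis, as described, protects that judgement.

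**Working it through.** The plan states no sample size, power, alpha or ICC, so there is no design figure to reproduce. The check asks what error rate the written model would have.

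**Sample size.** The Censoring Indicator paragraph gives "Approximately 10.3% ($n = 51$), 20.1% ($n = 100$) and 4.6% ($n = 23$) of participants reported lifetime alcohol use", marijuana use and intoxication, in that order. The only integer N from 200 to 1499 that returns all three rounded percentages is 497 (51/497 = 10.26%, 100/497 = 20.12%, 23/497 = 4.63%). Students at risk:
- alcohol: 497 − 51 = 446
- marijuana: 497 − 100 = 397
- intoxication: 497 − 23 = 474

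**Assumptions not in the documents.** Equal cluster sizes, a two-sided 5% test, and ICC from 0 to 0.05. Total clusters K = 8 (the four intervention communities plus four controls), 12 or 16.

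**Formulas.** With m = (students at risk)/K:
- DEFF = 1 + (m − 1) × ICC
- naive SE / correct SE = 1/√DEFF
- true type I error = 2 × [1 − Φ(1.96/√DEFF)]

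**Alcohol model, K = 8.** m = 446/8 = 55.75. At ICC 0.02, DEFF = 1 + 54.75 × 0.02 = 2.09. The naive SE is 0.69 of the correct one, and the true type I error is 17.6%.

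| ICC | DEFF, K = 8 | SE ratio, K = 8 | Type I error, K = 8 | K = 12 | K = 16 |
|---|---|---|---|---|---|
| 0 | 1.00 | 1.00 | 5.0% | 5.0% | 5.0% |
| 0.005 | 1.27 | 0.89 | 8.2% | 7.1% | 6.6% |
| 0.01 | 1.55 | 0.80 | 11.5% | 9.3% | 8.2% |
| 0.02 | 2.09 | 0.69 | 17.6% | 13.5% | 11.4% |
| 0.05 | 3.74 | 0.52 | 31.1% | 24.2% | 20.0% |

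With K = 8 and ICC 0.005 to 0.05, the range is 7.9% to 29.0% for marijuana and 8.5% to 32.2% for intoxication.

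**Simulation check.** The plan has "Data collection will consist of 4 longitudinal measurement occasions for each cohort using the adapted American Drug and Alcohol Survey", hence three risk periods. A cloglog hazard model with period terms, BUYOI, sex, age and two correlated perception scores, and no cluster term, was fitted to data with no true effect. Assumptions: 446 students, baseline hazard 0.10 per period, cluster SD 0, 0.15, 0.2, 0.3 or 0.4 on the cloglog scale, and 2,000 replicates each (Monte Carlo SE 0.5 to 1.0 points). Treatment exposure was left out because its coding is not given. ICC here is the observed ICC of any initiation over the three periods.
- 8 clusters (4 v 4): rejection 6.0% at ICC 0, 9.2% at about 0.007, 14.6% at 0.011, 20.6% at 0.024 and 29.6% at 0.043.
- 16 clusters (8 v 8), same cluster SDs: 5.3, 8.0, 9.0, 14.1 and 18.1%.
- A cluster-level t-test on the same data stayed between 4.3% and 5.8%.

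**Reference distribution.** Correcting the variance alone is not enough with few clusters. With 8 clusters the statistic has 6 degrees of freedom, and a 1.96 cut-off then rejects 9.8% even at DEFF = 1.

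**The case against.** The strongest reply is that silence is not a commitment to independence. The plan lists effects and covariates, not the variance method, and the analysts may have used a random effect or robust variance without saying so. That limits the finding to the model as written: it does not show what was run. It does not rescue the plan, because an unstated variance method can be chosen after the results are seen.

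The growth models are too thinly described to say that they ignore clusters. This is fair: the case is firmest for the hazard models. But a growth model ordinarily handles repeated measures within a student, and students within schools only if that level is added.

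Several points bear on size, not direction:
- **ICC value and scale.** No ICC is given, and the relevant one is what remains after covariates. At 0.001, with 8 clusters, the error is only 5.6%. The figures use the ICC on the observed scale; a separate simulation without covariates, with the ICC on the latent cloglog scale, gave 20.8% at 0.05 with 8 clusters.
- **Two cohorts.** If students in different cohorts of one cluster are correlated half as strongly as those in the same cohort, the 8-cluster alcohol figures fall from 17.6% to 14.6% at ICC 0.02 and from 31.1% to 26.1% at 0.05.
- **The 16-cluster case.** An 8 v 8 split needs more units than four intervention communities supply, unless schools were randomised separately. If communities were randomised, testing on schools is itself anti-conservative. With two schools per community and a community SD of 0.2 to 0.3 on the cloglog scale, a school-level t-test rejected 7% to 10%, against 4% to 5% at community level.
- **Remedy.** The cluster-level t-test was simulated; the random-intercept model with reduced degrees of freedom was not.

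**Conclusion.** The concern holds. The plan randomises clusters and, followed as written, analyses students as if they were independent. The direction of the error is certain for any positive residual ICC and vanishes only at zero. The size cannot be fixed from the documents. With 8 equal clusters and ICC 0.005 to 0.05, a nominal 5% test of BUYOI on alcohol initiation has a true error rate of about 8% to 31%; more clusters, a smaller ICC or weaker correlation between cohorts would lower it. The omission affects the intervention test in all three hazard models and must be corrected before any BUYOI p-value or interval is relied on. For the growth models, the finding is that nothing in the plan shows they account for clusters.

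**What to change.** State which unit was randomised and how many were allocated to each arm. Account for that unit in every model of the BUYOI effect, hazard and growth. Use a random intercept with small-sample degrees of freedom (clusters minus 2). If a variance estimated from few clusters proves unstable, use a cluster-level t-test or a permutation test over the allocation. Report the ICC for each outcome.

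The work is SAP wording and re-analysis in R, with no new data. The price is precision:
- **Interval width** relative to naive is √DEFF × t(0.975, K − 2)/1.96. With 8 clusters (t = 2.447) this is about 1.4 at ICC 0.005 and 2.4 at 0.05. With 16 (t = 2.145) it is about 1.2 and 1.7.
- **Power** for an effect that the naive SE credits with 80% comes from a noncentral t with noncentrality 2.80/√DEFF on K − 2 degrees of freedom. At ICC 0.005 / 0.01 / 0.02 / 0.05 it is about 55 / 47 / 37 / 23% with 8 clusters and 69 / 64 / 56 / 40% with 16. The naive 80% was never truly available: the t reference alone brings it to 65% at ICC 0 with 8 clusters.
- **Permutation** in a 4 v 4 design has 70 allocations, so two-sided p-values start at 2/70 = 0.029 and next reach 4/70 = 0.057. Only the most extreme split can reject at 5%.

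The 16-cluster figures apply only if the plan confirms that many separately randomised units.

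### Schools or communities are randomised, but the one BUYOI model with a stated covariate set does not handle clustering; its undefined treatment exposure covariate also needs defining

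*Combined protocol and SAP*

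**What the plan says.** The opening list of key features sets the design: "A randomized cluster design will be used where treatment schools receive an intervention targeted to 7th grade students, and control schools receive no intervention". The bullet on the training institute refers to "four communities randomly selected as intervention sites". The number of control clusters is not given, and the text does not settle whether school or community is the unit.

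Two analyses of the intervention effect are named. The data-collection bullet says "Longitudinal growth models will test for effects of the intervention on the targeted outcomes" and gives no outcome list, covariates or random-effect structure. Statistical Analysis says "we will use complementary log-log discrete time hazard models, implemented within R, to estimate the effects of BUYOI and the covariates" and sets out the tested terms: "the hypothesized main effects of BUYOI, gender, and perceived consequences of use for aspirations and autonomy controlling for age and treatment exposure". A second step adds a gender-by-treatment interaction. No section mentions a school or community effect, generalised estimating equations, robust variance, an intracluster correlation or a small-sample correction.

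Treatment exposure occurs once and is not among the variables under Measures. The nearest item is the Duration Variable, defined as "Duration of participation in media campaign intervention period across all four waves, beginning with the transition from first to second wave of data collection". The two terms are never linked, and no value is given for control students. Statistical Analysis also says "Each variable in the model is considered time-invariant for the purpose of this analysis". Measures dates age to baseline but gives no wave for the autonomy and aspiration scores, although these are what the campaign aims at: "The intervention uses older peers to deliver messages targeting the goals of autonomy and achievement (aspirations) associated with a drug-free life".

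**The concern.** When whole schools or communities are allocated, students in the same cluster share influences on initiation that have nothing to do with the campaign. A model that treats students as independent counts those shared differences as information about BUYOI. The estimated contrast is largely unaffected, but its standard error is too small and the test rejects too often. With four intervention clusters, a few unusual communities can look like a campaign effect. This matters in practice because the plan makes wide release of campaign materials depend on the intervention being found effective.

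The second question concerns what the BUYOI coefficient means. Dose received arises after randomisation and is absent in control schools. A model holding both arm and dose does not estimate the effect of being assigned to BUYOI. Whether treatment exposure is such a dose cannot be told from the text.

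**Working it through.** The documents state no sample size, power, alpha, intracluster correlation or effect size, so there is no design figure to reproduce. The baseline percentages can be checked.

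**Step 1: students at risk.** The Censoring Indicator paragraph gives 51 (10.3%), 100 (20.1%) and 23 (4.6%) lifetime users at baseline. 51/N rounds to 10.3% for N = 493-497, 100/N to 20.1% for 497-498, and 23/N to 4.6% for 495-505. Only N = 497 fits all three. At risk: 497 − 51 = 446 (alcohol), 497 − 100 = 397 (marijuana), 497 − 23 = 474 (intoxication).

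**Step 2: size of the clustering problem.** Assumed, not in the documents: 4 control clusters, equal cluster sizes, hazard h of 0.05 to 0.15 in each of three periods, and between-cluster SD s of 0 to 0.4 on the log hazard.

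- Expected events: d = N × [1 − (1 − h)³].
- Model variance of the log hazard ratio with equal arms: about 4/d.
- Variance missed by the model: s²/4 + s²/4 = s²/2.
- Ratio of true spread to model SE: r = √[1 + (s²/2)/(4/d)].
- True rejection rate at nominal 5%: 2 × [1 − Φ(1.96/r)].

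For N = 446 and h = 0.10: d = 446 × 0.271 = 120.9 and 4/d = 0.0331. At s = 0.2, r = √(1 + 0.02/0.0331) = 1.27, giving about 12%. At s = 0.4, r = √(1 + 0.08/0.0331) = 1.85, giving about 29%. The same formula at N = 446 for hazards 0.05 and 0.15 gives the second column below. The third comes from simulating the hazard model under a true hazard ratio of 1 (N = 446 at all three hazards; N = 397 and 474 at hazard 0.10).

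| Between-cluster SD | Formula, N = 446 | Simulation |
|---|---|---|
| 0 | 5% | about 5% |
| 0.1 | 6-8% | 6-7% |
| 0.2 | 9-15% | 8-15% |
| 0.3 | 14-25% | 13-24% |
| 0.4 | 19-35% | 20-37% |

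The ratio r runs from about 1.15 to 2.1 over SD 0.2-0.4. Crossing all three N with all three hazards moves the ends of the simulated ranges by no more than about 4 percentage points. A t test on the eight cluster summaries (6 df) stays near 5% throughout.

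**Step 3: treatment exposure, by reading.** Write the linear predictor as period terms + b × arm + g × exposure.

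- *Risk period or scheduled time, on the same footing in both arms.* b remains the contrast by arm. With a true hazard ratio of 0.60, simulation gives 0.60-0.64.
- *Dose entered raw, controls at 0, varying among treated students.* b compares treated students at zero dose with controls. If a share q of the log effect runs through dose, exp(b) is about 0.60 to the power (1 − q): 1.00 at q = 1, 0.77 at q = 0.5, 0.60 at q = 0. Simulation gives 0.95-1.06, 0.78-0.80 and 0.60-0.62.
- *Dose centred within the treated arm.* b is again close to the contrast by arm, 0.58-0.61 in simulation.

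Only the second reading does real damage, and only if some of the benefit runs through dose.

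**The case against.** A reader might infer that exposure adjustment is already shown to hide the campaign's effect. The documents do not support that. The Event Variable, Episodes, Duration Variable and Censoring Indicator paragraphs list the parts of a discrete-time model in turn. The Duration Variable starts at the move from wave 1 to wave 2, which matches the three risk periods, so exposure may be no more than elapsed period. The statement that all variables are time-invariant sits awkwardly with that reading, but it may describe only the predictors. A hazard ratio near 1 needs raw coding, a dose that varies among treated students and a wholly dose-driven benefit, none of which is stated. What stands is a gap in definition.

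A reader might also infer that ignoring clusters means the model fails to estimate the effect by assignment. That does not follow: clustering mainly affects standard errors and type I error, and is a separate matter from conditioning on exposure.

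The growth models might contain cluster terms, and the analysts might have added a random effect when fitting the hazard model. Both are possible, but the plan commits to neither. No between-cluster SD is given either, and at SD 0.1 the test rejects in only 6-7% of trials. That limits what can be said about size. It does not justify omitting the randomised unit.

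The perception scores may well be wave 1 values, since one value per student is used. The plan only needs to say so.

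**Conclusion.** The clustering point holds on every reading of treatment exposure. The design randomises clusters and the specified model takes no account of them, so its standard errors are too small if initiation varies between clusters at all. The size is illustrative: the stated rejection rates and the 1.15-2.1 ratio rest on 4 control clusters, equal cluster sizes, the assumed hazards and the assumed SDs. Only the at-risk counts are derived from the documents. No claim is made about this trial's actual type I error or power.

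The exposure point is conditional. The term is undefined and unlinked to the Duration Variable. Adjusting for it does little harm if it is risk period or scheduled time; if it is raw dose as described, the BUYOI coefficient is not the effect of assignment. The text does not decide between these. The undated autonomy and aspiration scores call for clarification and are not a demonstrated error.

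**What to change.** 1. Name the randomised unit, school or community, and give the number per arm.
2. For all three outcomes, base BUYOI inference on that unit with a few-cluster method that can keep the planned covariates and the gender-by-treatment term. Options are a cluster random effect, or cluster-robust variance with a small-sample correction, each with a t reference on cluster degrees of freedom; or covariate-adjusted cluster summaries, with the gender difference computed within each cluster and compared between arms.
3. Make the main estimate by assigned arm, with indicators for the three risk periods and no post-randomisation dose term.
4. Define treatment exposure (source, scale, timing, coding in control schools) and say whether it is the Duration Variable. Keep any dose analysis secondary and labelled non-randomised.
5. State that the autonomy and aspiration scores are wave 1 values.
6. Either specify the growth models to the same standard or say that they are not used for the BUYOI effect on initiation.

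The cost is SAP text, refitting of any model already run (Statistical Analysis partly uses the past tense), few degrees of freedom and wider intervals. With 4+4 clusters the critical value is 2.45 on 6 df, and 2.45/1.96 = 1.25. Combined with a standard error 1.15 to 2.1 times larger at SD 0.2-0.4, intervals would be about 1.25 × 1.15 = 1.4 to 1.25 × 2.1 = 2.6 times as wide as the unclustered model reports. No new data are needed for the main analysis if wave 1 scores were collected. The documents do not show that dose data exist, so a dose analysis may not be possible.
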